4 OBJECTIVES AND ENDPOINTS

The study objectives and endpoints are listed in the following 3 tables:

- Table 4-1: Objectives and endpoints that are specific to Cohort 1.
- [Table 4-2](#): Objectives and endpoints that are specific to Cohort 2.
- [Table 4-3](#): Objectives and endpoints that are common for both Cohort 1 and Cohort 2.

Additional endpoints and analyses will be described in the statistical analysis plan (SAP), the Endoscopy Image Review Charter, and/or the Histopathology Image Review Charter (as applicable). Selected endpoint definitions are provided in [APPENDIX 6](#).

Table 4-1: Objectives and Endpoints Specific to Advanced Therapy-naïve Cohort (Cohort 1)

Objectives	Endpoints
Primary 
• To explore the efficacy of ozanimod in inducing clinical response in the advanced therapy-naïve cohort.	Primary 
• Clinical response at Week 12, as measured by modified Mayo score.
Secondary 
• To explore the efficacy of ozanimod in the advanced therapy-naïve cohort.• To explore the effects of ozanimod on disease-specific HRQOL in the advanced therapy-naïve cohort.	Secondary 
• Clinical remission at Week 12, as measured by modified Mayo score.• Endoscopic response at Week 12.• Endoscopic improvement at Week 12.• Histological improvement at Week 12.• Change in the IBDQ total score from baseline to Week 12.• IBDQ response (change in total score [≥ 16 points] from baseline to Week 12).• IBDQ remission (total score [≥ 170 points]) at Week 12.

IBDQ, Inflammatory Bowel Disease Questionnaire.

Table 4-2: Objectives and Endpoints Specific to Advanced Therapy-exposed Cohort (Cohort 2)

Objectives	Endpoints
Primary 
To explore the efficacy of ozanimod in inducing clinical response in the advanced therapy-exposed cohort.	Primary 
Clinical response at Week 26, as measured by modified Mayo score.

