Secondary 
To explore the efficacy of ozanimod in the advanced therapy-exposed cohort.	Secondary 
Clinical remission at Week 26, as measured by modified Mayo score.Endoscopic response at Week 26.Endoscopic improvement at Week 26.Endoscopic remission at Week 26.Histological improvement at Week 26.Histological remission at Week 26.Change in the IBDQ total score from baseline to Week 26.IBDQ response (change in total score [\geq 16 points] from baseline to Week 26).IBDQ remission (total score [\geq 170 points]) at Week 26.Corticosteroid-free clinical remission at Week 26, as measured by modified Mayo score.HEMI at Week 26.

HEMI, histo-endoscopic mucosal improvement; IBDQ, Inflammatory Bowel Disease Questionnaire.

Table 4-3: Additional Objectives and Endpoints Common for both the Advanced Therapy-naïve Cohort (Cohort 1) and the Advanced Therapy-exposed Cohort (Cohort 2) after Week 26

Objectives	Endpoints

Secondary
 
• To explore the safety and tolerability of ozanimod in the advanced therapy-naïve cohort and the advanced therapy-exposed cohort.• To explore the long-term durability of response to ozanimod in the advanced therapy-naïve cohort and the advanced therapy-exposed cohort.	
Secondary
 
• Number and proportion of participants experiencing the following:
– AEs.– SAEs.– AEs and SAEs, including AEIs and other select AEs, leading to discontinuation from the study intervention and the study.– Clinical laboratory values.• Clinical remission by partial Mayo score at Weeks 52 and 104.• Corticosteroid-free clinical remission by partial Mayo score at Weeks 52 and 104.• Clinical response by partial Mayo score at Weeks 52 and 104.

Table 4-3: Additional Objectives and Endpoints Common for both the Advanced Therapy-naïve Cohort (Cohort 1) and the Advanced Therapy-exposed Cohort (Cohort 2) after Week 26

Objectives	Endpoints
AEI, adverse event of interest;	SAE, serious adverse event;

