7.7.2.1 Treatment Failure Rules

Treatment failure rules will be applied to the primary analyses of all efficacy endpoints. Participants will be considered to have failed treatment if any of the following occur:

- Any protocol-prohibited change in medications, including:
 - Post-baseline initiation of or increase in total daily dose to a level higher than the 40 mg maximum permitted dose of corticosteroid to treat UC.
 - Prolonged course of systemic corticosteroids (ie, > 12 consecutive weeks) for treatment of UC.
 - Initiation of an immune-suppressing therapy, including 6-mercaptopurine, AZA, methotrexate, anti-TNF agents, anti-integrin, anti-IL-12/23 agents, or JAK inhibitors.
- A colectomy (partial or total) or an ostomy.
- Discontinuation of the study intervention due to lack of therapeutic effect before primary or secondary efficacy evaluations.

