9.1.2.2 Health-related Quality of Life

HRQOL will be captured using the following questionnaires: [REDACTED] IBDQ, [REDACTED].

[REDACTED] The IBDQ was developed to measure the patient's experience of inflammatory bowel diseases (UC and CD). It consists of 32 questions divided into 4 dimensions: bowel symptoms (10 items), systemic symptoms (5 items), emotional function (12 items), and social function (5 items). Each question ranges from 1 "worst situation" to 7 "best situation"; and the total score ranges from 32 to 224, with higher scores representing better QOL.^{34,35} [REDACTED]

The timing of HRQOL collection is provided in the SOA (Section 2).

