10.3 Analysis Sets

For the purposes of analysis, the populations are defined as follows:

Population	Description
Enrolled	All participants who signed an ICF and were registered into IRT.
Cohort 1 Treated Analysis Population	All Cohort 1 participants who received at least one dose of study intervention. This population will be used for both the efficacy and safety analyses for Cohort 1.
Cohort 2 Treated Analysis Population	All Cohort 2 participants who received at least one dose of study intervention. This population will be used for both the efficacy and safety analyses for Cohort 2.
Defined Analysis Data Sets	Description
Analysis set for primary estimand (Cohort 1)	All Cohort 1-treated participants. Participants who discontinued study intervention and/or received prohibited concomitant medications prior to Week 12 will be considered non-responders.
Analysis set for primary estimand (Cohort 2)	All Cohort 2-treated participants. Participants who discontinued study intervention and/or received prohibited concomitant medications prior to Week 26 will be considered non-responders.

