10.4.3 Primary Endpoint

The primary endpoint for each cohort, their corresponding descriptions, and prespecified time points are listed in Table 10.4.3-1.

The primary endpoint for Cohort 1 is the proportion of participants who achieve a clinical response at Week 12. The clinical response rate at Week 12 will be estimated, and the corresponding 95% CI will be derived based on the Clopper Pearson method.

The primary endpoint for Cohort 2 is the proportion of participants who achieve a clinical response at Week 26. An estimate of the clinical response rate at Week 26 will be provided, along with the corresponding 95% CI derived based on the Clopper Pearson method.

For proportion-based efficacy endpoints, patients with missing Week 12 efficacy data from Cohort 1 and/or participants with missing Week 26 efficacy data from Cohort 2 will be considered non-responders, and non-responder imputation will be used. Sensitivity analyses around missing data may involve missing data imputed using multiple imputation and may analyze observed cases with no imputation. Details of the sensitivity analysis will be provided in the SAP.

For continuous efficacy endpoints, observed cases will be analyzed with no imputation.

Table 10.4.3-1: Endpoints

Primary	Description	Timeframe
Clinical Response (modified Mayo score)	Proportion of participants achieving the following: 
Decrease from baseline in the modified Mayo score of ≥ 2 points, andDecrease from baseline in the modified Mayo score of $\geq 35\%$, andDecrease in RB subscore of ≥ 1 point or absolute RB subscore ≤ 1.	Week 12 (Cohort 1) Week 26 (Cohort 2)
Secondary	Description	Timeframe
Clinical Remission (modified Mayo score)	Proportion of treated participants achieving the following in each component of the modified Mayo score: 
SF subscore ≤ 1, with ≥ 1-point decrease from baseline, andRB subscore = 0, andES ≤ 1.	Week 12 (Cohort 1) Week 26 (Cohort 2)
Endoscopic Response	Proportion of treated participants with a decrease from baseline of ≥ 1 point in Mayo ES	Week 12 (Cohort 1) Week 26 (Cohort 2)
Endoscopic Improvement	Proportion of treated participants with Mayo ES ≤ 1	Week 12 (Cohort 1) Week 26 (Cohort 2)

Table 10.4.3-1: Endpoints

Endoscopic Remission	Proportion of treated participants with Mayo ES = 0	Week 26 (Cohort 2)
IBDQ Response	Proportion of participants with a change from baseline in total score of ≥ 16 points	Week 12 (Cohort 1)

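### The treatment-failure rule and the observed-case rule are not reconciled for mean IBDQ change, so that mean may not represent all treated participants

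*Combined protocol and SAP*

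**What the plan says.** Section 7.7.2.1 states its scope without exception: "Treatment failure rules will be applied to the primary analyses of all efficacy endpoints". It then lists the failure events: prohibited medication changes (including starting another immune-suppressing therapy), colectomy or ostomy, and stopping study drug for lack of effect.

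Section 10.4.3, and the statistical methods paragraph of the Section 1 summary, give a separate rule: "For continuous efficacy endpoints, observed cases will be analyzed with no imputation".

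The continuous endpoint concerned is listed as secondary in both cohorts: "Change in the IBDQ total score from baseline to Week 12" (Table 4-1) and "Change in the IBDQ total score from baseline to Week 26" (Table 4-2). It is the only continuous secondary efficacy endpoint visible in Tables 4-1 to 4-3.

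Other provisions come close to the question but do not answer it:

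- Section 10.3 handles discontinuation and prohibited medication in binary terms only. For Cohort 1: "Participants who discontinued study intervention and/or received prohibited concomitant medications prior to Week 12 will be considered non-responders". Cohort 2 has the same rule at Week 26.
- Table 10.4.3-1 defines IBDQ response ("Proportion of participants with a change from baseline in total score of ≥ 16 points") and IBDQ remission, both of which fall under non-responder imputation. It has no row for the mean change, although Section 10.4.4 says the table holds all secondary endpoints.
- Missing-data sensitivity analyses are optional and appear in the paragraph on proportion-based endpoints: "Sensitivity analyses around missing data may involve missing data imputed using multiple imputation and may analyze observed cases with no imputation".

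**The concern.** Two analysts could each follow the protocol and report different mean IBDQ changes. One would read Section 10.4.3 alone and average every recorded value. The other would read Section 7.7.2.1 first and treat failures as failures, but would have to invent the value that a failure takes on this scale.

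The observed-case mean can depart from the all-treated mean in two ways. Participants with no value at Week 12 or Week 26 drop out of it. Participants who meet a failure rule but stay in follow-up may contribute a value that partly reflects the therapy they moved to.

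Quality of life is in the study title, and in a single-arm study there is no between-arm comparison in which such an error could partly cancel. The same questionnaire would also be summarised over different sets of participants: all treated for response and remission, only those with a value for the mean.

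**Working it through.** **1. The rules applied to three kinds of participant at the endpoint visit**

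- *No IBDQ value at the visit.* IBDQ response: non-responder. Mean change: left out.
- *Started another immune-suppressing therapy before the visit, value recorded.* IBDQ response: non-responder under Sections 7.7.2.1 and 10.3. Mean change: Section 10.4.3 alone counts the value as recorded; Section 7.7.2.1 says failure rules apply but gives no value or method.
- *Stopped study drug, still followed, value recorded.* IBDQ response: non-responder under Section 10.3. Mean change: the value is an observed case, and no rule says otherwise.

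The second case is the direct conflict. It needs no assumption about dropout.

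**2. The plan's own figures**

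The documents give no expected mean, standard deviation, missing rate or dropout rate for IBDQ change, so there is nothing to reproduce for this endpoint. The stated precision in Section 10.2 concerns the primary response rate. Its exact limits reproduce (75/150 gives 41.7% to 58.3%; 45/100 gives 35.0% to 55.3%) but have no bearing here.

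**3. Effect of missing values**

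Let d be the fraction of treated participants with no value, and let mO and mM be the mean changes in observed and missing participants.

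All-treated mean = (1 − d) × mO + d × mM

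Observed-case mean minus all-treated mean = mO − (1 − d) × mO − d × mM = d × (mO − mM)

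Both d and the gap (mO − mM) are assumptions. The gaps are set at multiples of the 16-point response threshold only to give a scale. Higher IBDQ is better ("the total score ranges from 32 to 224, with higher scores representing better QOL"), so a positive result means the observed mean is too favourable.

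| Missing (d) | Observed n, Cohort 1 / Cohort 2 | Gap −16 | Gap 0 | Gap 16 | Gap 32 |
|---|---|---|---|---|---|
| 10% | 135 / 90 | −1.6 | 0 | 1.6 | 3.2 |
| 20% | 120 / 80 | −3.2 | 0 | 3.2 | 6.4 |
| 30% | 105 / 70 | −4.8 | 0 | 4.8 | 9.6 |

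For example, 0.20 × 16 = 3.2 and 0.30 × 32 = 9.6. The observed n are 150 and 100 times (1 − d).

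**4. Effect of post-failure values**

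If a fraction f of the observed participants have values recorded after a failure event, and these exceed by h points the value a failure rule would assign, the mean shifts by f × h. With f = 10% and h = 16, that is 0.10 × 16 = 1.6 points. Both inputs are again assumptions, and h is undefined until the protocol says what a failure is worth.

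**5. What each analysis needs**

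The observed-case mean equals the all-treated mean in expectation only if missingness is unrelated to the change. A repeated-measures model needs missingness to be unrelated to the unseen value once baseline and earlier IBDQ scores are taken into account, which is a weaker requirement. Table 2-1 already schedules the IBDQ on Day 1 and at Weeks 4, 12 and 26.

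**The case against.** The strongest reply is that the two rules address different things: the observed-case rule is about missing data, the failure rules about events on treatment, so both can be followed. That is right as far as it goes. It shows that the rules could be reconciled, but nothing in the text does so, because no section gives a failure a value on a continuous endpoint.

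A reader might infer that the mean is estimated in completers. The documents do not support that. Section 8.1 keeps participants who ask to stop treatment in the study and in follow-up, Section 8.2.1 says that stopping treatment is not withdrawal, and the IBDQ is scheduled at the early-termination visit. Section 8.1.2 is weaker and makes follow-up optional, and no rule says whether an early-termination value stands in for Week 12 or Week 26. But observed cases are everyone with a value, not those who finished treatment.

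A reader might also infer that the mean is biased upward. That direction is plausible if people leave because they are doing badly, or if rescued participants improve on other therapy. It is not shown: the table above includes zero and negative values, and no figure in the documents selects among them. Nor do the documents say that post-failure values are kept; they are silent.

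Three further points stand as mitigation. IBDQ response and remission already give an all-treated, conservative reading of the same questionnaire, although they do not estimate the mean. Section 10.4.1 reports n with continuous summaries, so missing values will be visible. Section 10.4.4 defers secondary-endpoint detail to an SAP whose text is not in the document reviewed; if it settles the matter, the point is met. Deferral alone does not settle it, because the protocol has already stated two rules that collide.

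**Conclusion.** The inconsistency between Sections 7.7.2.1 and 10.4.3 is real for mean IBDQ change in both cohorts and follows from the text alone. As written, participants without a value leave the mean, and the treatment of post-failure values is undefined, so the result may not represent all treated participants.

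The size and direction of any error are not established. Under the assumed 10% to 30% missing, the error is 1.6 to 9.6 points too favourable for gaps of 16 to 32 points, zero for no gap, and 1.6 to 4.8 points too unfavourable if missing participants did 16 points better. The 16-point threshold is an individual-response cut-off and serves here only as a scale.

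The consequence is limited: one descriptive secondary endpoint, no hypothesis test, and primary endpoints protected by non-responder imputation. It is still worth settling in advance, because a rule chosen after the data are seen would leave the estimate open to challenge.

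**What to change.** - Reconcile Sections 7.7.2.1 and 10.4.3 before database lock by stating how a treatment failure is handled for mean IBDQ change, including whether values recorded after the event are used. The model below does not decide this by itself.
- Estimate the mean change with a repeated-measures model using Weeks 4 and 12 in Cohort 1 and Weeks 4, 12 and 26 in Cohort 2, with baseline IBDQ as covariate. Evaluate it at the baseline mean of all treated participants.
- Keep the observed-case summary beside it, with observed n reported against treated n.
- Prespecify one sensitivity analysis that counts failures unfavourably. Setting their change to zero is simple but would flatter anyone who worsened; the lower of zero and the participant's worst recorded change avoids that.
- Add mean IBDQ change to Table 10.4.3-1.

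The cost is SAP wording and one extra model per cohort, with no new data. Section 10.4 lets the SAP modify these plans and asks for a protocol amendment only for major changes to key endpoints or their analyses. The model relies on a missing-at-random assumption, which is weaker than what observed cases need, and participants with no post-baseline IBDQ contribute only through their baseline score.

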10.4.4 Secondary Endpoints

All secondary endpoints, their corresponding descriptions, and prespecified time points are listed in [Table 10.4.3-1](#) for each cohort.

For all binary response secondary endpoints in each cohort, the response rate at the prespecified time point will be estimated and a corresponding 95% CI will be derived based on the Clopper Pearson method. Details of the analysis for each secondary endpoint will be specified in the SAP.

10.4.6 Other Safety Analyses

All safety analyses will be carried out for the treated population.

AEs will be monitored during the study, and the data will be analyzed with respect to incidence, severity, and the potential relationship of the AEs and study intervention. AEs with onset on or after the first dose of study intervention, or with onset prior to the first dose of study intervention that increase in severity on or after the first dose of study intervention will be considered treatment-emergent. TEAEs will be summarized for the safety population by system organ class (SOC) and preferred term, and presented in descending order of frequency within each SOC. SAEs, including AEIs, and AEs leading to discontinuation of study intervention will be summarized similarly.

Laboratory parameters will also be summarized. For each laboratory test, individual participant values outside the standard reference range will be flagged and listed. Shift tables will be produced showing the frequency of shifts from baseline to the lowest and to the highest on-trial value in and out of the normal range, as well as by visit. Changes from baseline to each visit for each laboratory parameter will also be summarized.

The change from baseline to each visit for each of the vital sign variables will be summarized. Abnormal vital sign values will be flagged and listed.

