8 DISCONTINUATION CRITERIA

8.1 Discontinuation From Study Intervention

Participants MUST discontinue IP for any of the following reasons:

- Participant's or investigator's request to stop study intervention. Participants who request to discontinue study intervention will remain in the study and must continue to be followed for the protocol-specified follow-up procedures. The only exception to this is when a participant specifically withdraws consent for any further contact with him/her or persons previously authorized by the participant to provide this information.
- Any clinical AE, laboratory abnormality, intercurrent illness, or other appropriate reason(s), which, in the opinion of the investigator, indicates that continued administration of study intervention is not in the best interest of the participant.
- Termination of the study by BMS.
- Loss of ability to freely provide consent through imprisonment or involuntarily incarceration for treatment of either a psychiatric or physical (eg, infectious disease) illness. (Note: Under specific circumstances and only in countries where local regulations permit, a participant who has been imprisoned may be permitted to continue as a participant. Strict conditions apply, and BMS approval is required.)

- Pregnancy (refer to [Section 9.2.5](#)).
- Significant non-compliance with the protocol (eg, procedures, assessments, medications). The investigator should discuss such issues with the Medical Monitor.
- Participant meets one of the following criteria for laboratory abnormalities in 2 sequential laboratory measurements taken up to 14 days apart:
 - Hb < 7.0 g/dL or a decrease of >30% from baseline
 - Lymphocyte count < $0.2 \times 10^9/\text{L}$ ($< 200/\text{mm}^3$) – see [Section 9.2.6](#) for temporary discontinuation guidance.
- Participant meets any of the following criteria for liver-related laboratory abnormalities. If these abnormalities are identified, repeat testing should occur within 48 to 72 hours, and these results should be discussed with the BMS Medical Monitor or designee. Additional recommendations on the recognition and investigation of potential drug-induced liver injury (DILI) are given in [Section 9.2.7](#).
 - ALT or AST > $8 \times \text{ULN}$ on a single occasion.
 - ALT or AST > $5 \times \text{ULN}$ for more than 2 weeks.
 - ALT or AST > $3 \times \text{ULN}$ and total bilirubin > $2 \times \text{ULN}$ or international normalized ratio (INR) > 1.5.

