 - ALT or AST > $3 \times \text{ULN}$ with the appearance of fatigue, nausea, vomiting, right upper quadrant pain or tenderness, fever, rash, and/or eosinophilia (> 5%).

Refer to the SOA for the data that will be collected at the time of treatment discontinuation and follow-up and for any further evaluations that can be completed.

All participants who discontinue study intervention should comply with the protocol-specified follow-up procedures, as outlined in [Section 2](#). The only exception to this requirement is when a participant withdraws consent for all study procedures, including post-treatment study follow-up, or loses the ability to consent freely (eg, is imprisoned or involuntarily incarcerated for the treatment of either a psychiatric or physical illness).

If study intervention is discontinued prior to the participant's completion of the study, the reason for the discontinuation must be documented in the participant's medical records, per local regulatory requirements in each region/country, as applicable, and entered on the appropriate eCRF page.

8.1.1 *Treatment Interruption*

Participants should be instructed that if they forget to take a dose, they can take it within 4 hours of the normal dosing time; otherwise, they should take their next dose at the regular time on the following day. If the participant vomits the dose, he/she should be instructed not to take another dose on the same day, but to take the next dose at the regular time on the following day. Participants will record whether they took the daily dose of medication in an electronic diary that will be reviewed periodically by the site staff and the site monitor.

If a dose is missed during the first 2 weeks of treatment, re-initiate treatment using dose escalation regimen. If a dose of study intervention is missed after the first 2 weeks of treatment, continue with the treatment as planned. If more than 7 consecutive days between Day 15 and Day 28 of treatment, or more than 14 consecutive days after Day 28 of treatment, re-initiate treatment using the dose escalation regimen. The Medical Monitor should be contacted to discuss completing the dose escalation schedule.

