8.1.2 Post-study Intervention Study Follow-up

Participants who discontinue study intervention may continue to be followed.

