8.2.1 Individual Discontinuation Criteria

- A participant may withdraw completely from the study at any time at his/her own request, or may be withdrawn at any time at the discretion of the investigator for safety, behavioral, compliance, or administrative reasons; this is expected to be uncommon. Stopping study intervention is not considered withdrawal from the study.
- At the time of discontinuing from the study, the end of treatment and follow-up visits should be conducted, if possible, as shown in the SOA. See the SOA ([Table 2-1](#) and [Table 2-2](#)) for the data to be collected at the time of study discontinuation and follow-up and for any further evaluations that need to be completed.
- The participant will be permanently discontinued both from the study intervention and from the study at that time.
- If the participant withdraws consent for disclosure of future information, the Sponsor may retain and continue to use any data collected before such a withdrawal of consent.

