9.2.1 Time Period and Frequency for Collecting AE and SAE Information

The collection of nonserious AE and coronavirus disease (COVID) AE information should begin at screening until the follow-up visit, at the time points specified in the SOA ([Section 2](#)).

All SAEs must be collected from the time of signing the ICF, including those thought to be associated with protocol-specified procedures, and within 30 days following discontinuation of dosing.

The investigator must report any SAE that occurs after these time periods and that is believed to be related to study intervention or a protocol-specified procedure (eg, endoscopy, biopsy).

- Medical occurrences that begin before the start of study intervention but after obtaining informed consent will be recorded in the appropriate section of the eCRF.
- All SAEs will be recorded and reported to the Sponsor or designee within 24 hours, as indicated in [APPENDIX 5](#).
- The investigator will submit any updated SAE data to the Sponsor or designee within 24 hours of the updated information being available.

Investigators are not obligated to actively seek AEs or SAEs in former study participants. However, if the investigator learns of any SAE, including a death, at any time after a participant has been discharged from the study, and he/she considers the event to be reasonably related to the study intervention or study participation, the investigator must promptly notify the Sponsor.

The method of evaluating and assessing causality of AEs and SAEs, and the procedures for completing and reporting/transmitting SAE reports are provided in [APPENDIX 5](#).

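### The treatment-emergent definition has a start but no end, so chiefly nonserious events that begin off ozanimod or on a successor UC therapy are counted as ozanimod TEAEs

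*Combined protocol and SAP*

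**What the plan says.** Section 10.4.6 has two routes to a TEAE. The first is "AEs with onset on or after the first dose of study intervention". The second covers events that began before the first dose "that increase in severity on or after the first dose of study intervention will be considered treatment-emergent". Neither has an upper limit, and no rule says what happens once another UC therapy starts. The same section builds the laboratory shift tables from "shifts from baseline to the lowest and to the highest on-trial value", as well as by visit.

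The follow-up rules decide how long the open window can run:

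- Section 8.1, repeated in 8.2: "Participants who request to discontinue study intervention will remain in the study and must continue to be followed for the protocol-specified follow-up procedures", unless consent to contact is withdrawn.
- Section 8.1, for everyone who stops drug: "All participants who discontinue study intervention should comply with the protocol-specified follow-up procedures, as outlined in" Section 2, the Schedule of Activities.
- Section 8.1.2, in weaker terms: "Participants who discontinue study intervention may continue to be followed".
- Section 8.2.1: "Stopping study intervention is not considered withdrawal from the study".
- Section 9.2.1, for nonserious and COVID AEs: "AE information should begin at screening until the follow-up visit". SAEs are collected from consent to 30 days after dosing stops. Later SAEs are required only if thought related to ozanimod or to a protocol procedure.
- Table 2-2: the end-of-treatment or early-termination visit is at Week 104 (Day 728) and post-treatment follow-up is at Week 116 (Day 812). AE and SAE monitoring are marked at both.

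**The concern.** Safety and tolerability is a stated secondary objective (Table 4-3), and there is no control arm against which to judge the event rates. With no end date, a nonserious infection that begins well after the last capsule, possibly while the participant takes another biologic, enters the main ozanimod TEAE table as an ozanimod event. The reported proportion then mixes drug risk with the risks of active disease and of the next therapy. How far it does so depends on how many participants stop and how long sites follow them.

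Section 7.7.2.1 makes the start of another immune-suppressing therapy a treatment failure for efficacy. Nothing equivalent exists on the safety side.

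**Working it through.** The plan states no TEAE window, TEAE rate or off-drug exposure, so there is no figure to reproduce. The check compares the passages and then does day arithmetic on the schedule.

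**1. Does any rule close the window?** Section 10.4.6 does not. Section 9.2.1 does so indirectly for unrelated SAEs, because routine collection stops at last dose + 30 days. For nonserious AEs, collection ends at the follow-up visit, which is not defined relative to the last dose.

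**2. Schedule.** 104 × 7 = Day 728 and 116 × 7 = Day 812. A completer therefore has 812 − 728 = 84 off-drug days inside the TEAE window. Against the 30-day SAE rule, 84 − 30 = 54 of those days fall after routine SAE collection has ended, yet Table 2-2 still marks SAE monitoring at Week 116.

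**3. Off-drug days for a participant who stops early.** Two readings are possible.

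- *Short reading:* an end-of-treatment visit when drug stops, then a follow-up visit 12 weeks later. Off-drug time is about 12 × 7 = 84 days, before visit windows.
- *Long reading:* scheduled visits continue to Day 812. Off-drug time is 812 − stop day:

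| Stop day | Off-drug days | Of which more than 90 days after last dose |
|---|---|---|
| 84 | 728 | 638 |
| 182 | 630 | 540 |
| 365 | 447 | 357 |

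The 90-day comparison uses the protocol's post-treatment contraception interval (Section 6.3).

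**4. Share of follow-up time, under assumptions.** The documents give no discontinuation rate. Assume that a fraction d stops, uniformly over Days 1 to 728 (mean Day 364.5), and that the rest complete.

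- *Long reading:* share = [d × (812 − 364.5) + (1 − d) × 84] / 812. For d = 0.20: (89.5 + 67.2) / 812 = 19%. For d = 0.50: (223.75 + 42) / 812 = 33%.
- *Short reading:* share = 84 / [d × (364.5 + 84) + (1 − d) × 812]. For d = 0.20: 84 / 739.3 = 11%. For d = 0.50: 84 / 630.25 = 13%.

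These are shares of follow-up time, not event rates.

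**5. Laboratory tables.** Table 2-2 schedules blood count and biochemistry at Week 104 but not at Week 116. Off-drug values can enter the lowest and highest on-trial value in three ways: later scheduled visits of an early stopper (long reading), unscheduled tests, or the repeat testing that Section 9.2.6 requires after permanent discontinuation for a confirmed low lymphocyte count.

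**The case against.** The best counter-argument is that the study already limits the damage.

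- **SAEs.** A reader might infer that all late events, serious ones included, are counted. Section 9.2.1 does not support that: an unrelated SAE more than 30 days after dosing stops need not be collected. This stands, and it confines the point chiefly to nonserious events. The Week 116 SAE mark in Table 2-2 remains unreconciled with it.
- **Length of follow-up.** A reader might infer that every discontinuer is followed to Day 812. Section 8.1.2 says only that they *may* be followed, the Week 104 column doubles as the early-termination visit, and Section 9.2.6 speaks of testing after the end-of-treatment visit in people who stopped drug for good. All of this favours the short reading. Against it, Sections 8.1 and 8.2 say *must* for those who ask to stop, and the Table 2-2 footnote on early visits concerns leaving the study, which Section 8.2.1 distinguishes from stopping drug. The text does not settle the matter.
- **Laboratory values.** With no Week 116 laboratory tests scheduled, wide contamination of the shift tables cannot be inferred. The repeat lymphocyte tests follow an abnormality that arose on ozanimod and are relevant to it.
- **Causality.** Section 10.4.6 also analyses relationship to study drug, and Appendix 5 asks investigators to weigh concomitant therapy and underlying disease. That helps interpretation but takes no event out of the TEAE counts.
- **Deferral.** Section 10.4 leaves detail to a SAP due before database lock. A cut-off could be added there, but the documents supplied contain none, and Section 10.4.6 as written is already a complete working rule.

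**Conclusion.** The point holds in limited form. Applied as written, Section 10.4.6 counts as ozanimod TEAEs those events, chiefly nonserious, that begin off drug or on a successor UC therapy. The off-drug time counted per discontinuer is about 84 days on the short reading. On the long reading it is 728 days for a stop at Day 84. On the short reading the excess nearly disappears if an 84-day lag is adopted, though events after a therapy switch would still go unflagged.

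A reader might go further and put a number on the participants affected, or conclude that the two cohorts' TEAE proportions will be distorted unequally. The documents give no discontinuation rate, switching rate or infection rate for either cohort, so neither inference is supported. The 11% to 33% range in the working rests on assumed discontinuation of 20% to 50%, spread evenly over time, and describes follow-up time only. Confidence is medium, because the size depends on follow-up rules that the protocol states inconsistently.

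**What to change.** 1. In Section 10.4.6, define a TEAE as onset or worsening from first dose through last dose plus one stated lag. The Week 104 to Week 116 interval, 84 days, is one candidate. The protocol also uses 30 days (SAE collection) and 90 days (contraception), so give the reason for the choice.
2. Align the AE and SAE collection windows in Section 9.2.1 and Table 2-2 with that lag. An 84-day TEAE window over 30-day SAE collection would leave unrelated SAEs from days 31 to 84 incompletely captured. If the SAE window stays at 30 days, summarise SAEs through last dose plus 30 days and say so.
3. Reconcile Sections 8.1 and 8.2 with Section 8.1.2 and the Table 2-2 visit headings, so that follow-up after stopping drug is stated once.
4. Tabulate events after the cut-off separately as post-treatment, and flag events with onset after the start of another advanced UC therapy.
5. In the shift tables, replace the on-trial extremes with values through the same cut-off. This matters mainly for early stoppers who have later scheduled or unscheduled tests.

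The cost is protocol and SAP wording plus one extra table. Intervention stop dates (Section 7.6) and UC medications (Tables 2-1 and 2-2) are already recorded, and the present definition already needs AE onset dates. The downside is that late-onset events leave the main table, so the post-treatment table must be reported beside it.
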